1 STATEMENT OF COMPLIANCE

The trial will be carried out in accordance with International Conference on Harmonisation Good Clinical Practice (ICH GCP) and the following:

- United States (US) Code of Federal Regulations (CFR) applicable to clinical studies (45 CFR Part 46, 21 CFR Part 50, 21 CFR Part 56, 21 CFR Part 312, and/or 21 CFR Part 812)

All site staff responsible for the conduct, management, or oversight of the study has completed Human Subjects Protection Training.

The protocol, informed consent form(s), recruitment materials, and all participant materials will be submitted to the Institutional Review Board (IRB) for review and approval. Approval of both the protocol and the consent form must be obtained before any participant is enrolled. Any amendment to the protocol will require review and approval by the IRB before the changes are implemented to the study. In addition, all changes to the consent form will be IRB-approved; a determination will be made regarding whether a new consent needs to be obtained from participants who provided consent, using a previously approved consent form.

2b: We hypothesize that aqueous obtained at the time of a recurrence of inflammation will demonstrate a detectable viral load and will correlate with level of inflammation.

Specific Aim 3 (samples from Trials I and II): To characterize host transcriptional signatures and viral genomic features in CMV anterior uveitis using RNA sequencing of aqueous samples.

3a: We hypothesize participants completing both trials who exhibit recurrent inflammation after antiviral suppression (Trial II) will have a higher prevalence of CMV mutations associated with antiviral resistance compared to baseline samples (Trial I).

3b: We hypothesize that (i) host transcriptional profiles will distinguish CMV anterior uveitis from anterior uveitis cases negative for CMV and unable to enter Trial I, (ii) we will identify non-CMV pathogens in cases unable to enter Trial I, and (iii) we will identify unique signatures associated with recurrent inflammation in Trial II participants.

Study Population:

We plan to enroll 117 participants (39 participants per arm) across all sites.

Description of

Sites/Facilities

Enrolling

Participants:

Participants will be enrolled at 6 sites centered in the United States, Thailand and Taiwan. In Thailand, participants will be enrolled at Chulalongkorn University in Bangkok, Thailand, Khon Kaen University in Khon Kaen, Thailand and Chiang Mai University in Chiang Mai, Thailand. In Taiwan, participants will be enrolled at

Chang Gung Memorial Hospital. In the United States, participants will be enrolled at the Francis I. Proctor Foundation/UCSF and the University of California, Los Angeles. UCSF will serve as the clinical and data coordinating center.

Outcomes:

Trial I: Primary Endpoint: Viral load after 7 days of treatment

Secondary Endpoints:

- Clinical quiescence

Trial II: Primary Endpoint: Recurrence of inflammation over 12 months

Secondary Endpoints:

- Prevalence of mutations conferring antiviral resistance

Schema

Trial I

Pre-study visit (Exam 0)

Clinical eye examination reveals active anterior uveitis ($\geq 1+$ AC cell) and suggests a viral aetiology

[figure not shown]
- **Anterior chamber paracentesis** is performed to establish a viral aetiology
 - Half of fluid will be used for in- house directed PCR for HSV, VZV and CMV
 - At least 50 μ L of fluid will be preserved and used for quantitative CMV PCR to be conducted at a single US laboratory in eligible participants
- Laboratory screening orders (CBC, chemistry panel, pregnancy test, HIV status)
- Patients will be prescribed topical corticosteroid (prednisolone acetate 1%) to be used one drop in affected eye four times per day (this is typical standard of care)
- Patients requiring management of elevated IOP will be prescribed IOP-lowering medication according to treating ophthalmologist's discretion and best medical judgment

Exam 1 Randomization and Procedures

[figure not shown]
- Review of results of in- house CMV PCR and laboratory results
- Consent, enrollment, randomization to treatment arm if participants meet eligibility criteria
- Clinical eye examination (in the following order: visual acuity, slit lamp examination of anterior segment, intraocular pressure assessment, confocal microscopy)

Randomization to 1 of 3 arms

Exam 2 (Day 7) Follow-up

- Clinical eye examination (in the following order: visual acuity, slit lamp examination of anterior segment, intraocular pressure assessment)
- **Anterior chamber paracentesis #2**
- **Assessment of clinical quiescence (grading anterior chamber cell)**
- Laboratory monitoring orders (complete blood count, complete metabolic panel)

Exam 3 (Day 21) Final visit for trial I

Trial II

**Exam 1
(Re-randomization)**

Clinically inactive (< 1+ anterior chamber cell)
for at least 2 weeks with at least 2 weeks
wash-out period (no antivirals)

- Clinical eye examination (in the following order, VA, slit lamp examination of anterior segment, IOP)
- **Suppressive treatment initiation (randomized to 1 of 3 arms)**

Group 1: Oral
valganciclovir N=35

Group 2: Topical
ganciclovir 2% N=35

Group 3: Placebo
N=35

**Exam 2
(1 month after
randomization)**

- Clinical eye examination (in following order, VA, slit lamp examination of anterior segment, IOP)
- **Assessment for recurrence of inflammation**
- **Anterior chamber paracentesis #3 if recurrent inflammation (participant exits study if recurrent inflammation)**

**Exam 3
(3 months after
randomization)**

- Clinical eye examination (in following order, VA, slit lamp examination of anterior segment, IOP)
- **Assessment for recurrence of inflammation**
- Confocal or specular microscopy if recurrent
- **Anterior chamber paracentesis #3 if recurrent inflammation (participant exits study if recurrent inflammation)**

**Exam 4
(5 months after
randomization)**

- Clinical eye examination (in following order, VA, slit lamp examination of anterior segment, IOP)
- **Assessment for recurrence of inflammation**
- Confocal or specular microscopy if recurrent
- **Anterior chamber paracentesis #3 if recurrent inflammation (participant exits study if recurrent inflammation)**

**Exam 5
(7 months after
randomization)**

- Clinical eye examination (in following order, VA, slit lamp examination of anterior segment, IOP)
- **Assessment for recurrence of inflammation**
- Confocal or specular microscopy if recurrent
- **Anterior chamber paracentesis #3 if recurrent inflammation (participant exits study if recurrent inflammation)**

**Exam 6
(9 months after
randomization)**

- Clinical eye examination (in following order, VA, slit lamp examination of anterior segment, IOP)
- **Assessment for recurrence of inflammation**
- Confocal or specular microscopy if recurrent
- **Anterior chamber paracentesis #3 if recurrent inflammation (participant exits study if recurrent inflammation)**

**Exam 7
(11 months after
randomization)**

- Clinical eye examination (in following order, VA, slit lamp examination of anterior segment, IOP)
- **Assessment for recurrence of inflammation**
- **Anterior chamber paracentesis #3 if recurrent inflammation (participant exits study if recurrent inflammation)**

Exam 8
(12 months after
randomization,
Final Visit)

- Clinical eye examination (in the following order, VA, slit lamp examination of anterior segment, IOP)
- **Assessment for recurrence of inflammation**
- **Anterior chamber paracentesis #3 if recurrent inflammation (participant exits study if recurrent inflammation)**

Note that participants will be advised to contact their local site clinical coordinator or study ophthalmologist if they are having symptoms of recurrent inflammation. Recurrent inflammation is typically symptomatic (characterized by ocular redness, decreased vision, light sensitivity, and pain). Thus, participants will be evaluated for symptoms of recurrent inflammation, which may occur between study visits, during which they would have clinical eye examination, anterior chamber paracentesis #3 (if there is recurrent (active) inflammation).

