4 STUDY DESIGN

4.1 Overall Design

The Systemic and topical antiviral control of cytomegalovirus anterior uveitis: treatment outcomes (STACCATO) study will enroll participants with PCR-proven CMV anterior uveitis into a sequential double-masked randomized clinical trial in the US and Asia. In Trial I, participants will be randomized to one of the three treatment groups:

Group 1: Valganciclovir tablets 900 mg PO BID (4 tablets daily) and Placebo drops 1 drop 6 times daily

Group 2: Topical ganciclovir 2% 1 drops 6 times daily and Placebo tablets 2 tablets PO BID (4 tablets daily)

Group 3: Placebo tablets 2 tablets PO BID (4 tablets daily) and Placebo drops 1 drop 6 times daily

After participants achieve control of their inflammation, they will enter Trial II at which point they will be re-randomized to one of the three arms in Trial I at a prophylactic dosing. Additionally, patients with known CMV anterior uveitis, but who are inactive, may enter Trial II directly. Recurrences of inflammation in Trial II will be assessed for presence of detectable viral load. Those who agree to participate will be randomized at baseline and after achieving clinical quiescence, get re-randomized to one of the three treatment groups:

Group 1: Valganciclovir tablets 450 mg PO BID (2 tablets daily) and Placebo drops 1 drop BID

Group 2: Topical ganciclovir 2% 1 drop BID and Placebo tablets 1 tablet PO BID (2 tablets daily)

Group 3: Placebo tablets 1 tablet PO BID (2 tablets daily) and Placebo drops 1 drop BID

All study ophthalmologists and participants will remain masked to treatment assignment after enrollment. Due to the treatment design, all participants will receive both pills and eye drops. An interim analysis will be performed for both trials once primary outcome data is available for one third of the patients.

4.1.1 . STUDY MASKING PROCEDURES (EXAM #2 AND 3)

- The patient comes for the study visit and meets with the study coordinator before seeing their study doctor. This will facilitate masking of ophthalmologists and participants. All outcome assessors including lab technicians for trial I and ophthalmologists for trial II will remain masked. To facilitate interim and safety analysis, a data team member may also be unmasked.
- The patient's medication bottles are immediately placed in a secure, black bag and left at the study coordinators desk for the remainder of the visit. Patient medication calendars should also be placed in the black bag.

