5 STUDY POPULATION

5.1 Inclusion Criteria

In order to be eligible to participate in Trial I of this study, an individual must meet all of the following criteria:

- CMV positivity by nucleic acid amplification test (e.g., polymerase chain reaction) from aqueous humor obtained via anterior chamber paracentesis obtained during an active flare of inflammation (uveitis) preceding enrollment into study
- Active anterior uveitis using Standardisation of Uveitis Nomenclature (SUN) Working group with clinical impression of CMV as the etiologic agent defined as $\geq 1+$ anterior chamber cell²¹
- Participant willingness to use an acceptable method of contraception during the study period (i.e., pharmacologic, barrier methods or abstinence).
- Age over 18 years
- Basic understanding of the study as determined by the physician
- Commitment to return for follow up visits

To be eligible for Trial II, an individual must:

- Have a history of being CMV positive by nucleic acid amplification test (e.g., polymerase chain reaction) from aqueous humor obtained via anterior chamber paracentesis during an active flare of inflammation (uveitis)
- Have inactive inflammation ($< 1+$ anterior chamber cell) for at least 2 weeks
- Have a period of 2 weeks of no antiviral prior to long-term treatment initiation

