5.2 Exclusion Criteria

An individual who meets any of the following criteria will be excluded from participation in this study:

Trial I

- Negative for CMV by nucleic acid amplification test (e.g., polymerase chain reaction) of aqueous humor obtained via anterior chamber paracentesis during an active flare of inflammation (uveitis) preceding enrollment into study
- Participants <18 years of age
- Inactive anterior uveitis
- Active intermediate or posterior inflammation (involvement of vitreous, choroid or retina)
- Participants who have received antiviral therapy <14 days prior to enrolment
- Participants who have received periocular or intraocular corticosteroid injection <8 weeks prior to enrolment
- Current use of oral corticosteroids
- Immunocompromised participants (primary or secondary immunodeficiency disorders)
- Prior immunosuppressive therapy in the past 3 months
- Directed PCR testing positive for HSV or VZV
- Plans to conceive during the study period, pregnant or breastfeeding mothers (blood or urine pregnancy test for all females of childbearing age is mandatory within 4 weeks prior to enrolment)
- Complete blood count with white blood cell, absolute neutrophil or platelet count lower than the lower limit of reference laboratory normal
- Blood urea nitrogen or creatinine above the upper limit of reference laboratory normal
- Recent ocular surgery within the past 30 days or planned surgery within the next 45 days
- Systemic autoimmune disease or ocular condition (besides anterior uveitis) anticipated to dictate or alter treatment course

In Trial II, participants will be excluded if

- They have not had prior positive CMV by nucleic acid amplification test (e.g., polymerase chain reaction) of aqueous humor obtained via anterior chamber paracentesis during active flare of inflammation (uveitis)
- Have active inflammation
- Did not have a 2-week period of no antiviral (treatment) prior to randomization to long-term prophylaxis

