## 6. Analysis

### 6.1. Outcome definitions

Trial I: Primary Endpoint: Log-transformed viral load after 7 days of treatment

Secondary Endpoints:

- Anterior chamber cell (days 7, 21)
- Intraocular pressure (days 7, 21)
- Visual acuity (days 7, 21)
- Controlled inactivity defined as  $\leq 0.5+$  anterior chamber cell AND intraocular pressure  $< 24$  mmHg AND no cornea edema AND no active KPs (day 7, 21).

Trial II: Primary Endpoint: Proportion recurrent inflammation ( $\geq 1+$  anterior chamber cell at any study visit) over 12 months

Secondary Endpoints:

- Prevalence of CMV associated with recurrence of uveitis

1a. The Aim 1 primary outcome **viral load after 7 days of treatment** will use the results from quantitative PCR at 7 days of treatment or placebo therapy (day 7 of trial). All quantitative PCR viral loads will undergo base-10 logarithm-transformation, with units converting from IU/mL to log IU/mL. Log-transformed viral loads will be used because the range of viral loads can be wide and dealing with very large and very small numbers is handled more efficiently using a logarithmic scale. Such normalization of the distribution of viral loads is consistent with standard practice in viral load analyses.

1b. **Clinical outcomes and inactivity:** At each study visit participants will be clinically examined for ocular outcomes including AC inflammatory cells, intraocular pressure, and visual acuity. A study ophthalmologist will make a clinical determination as to whether the patient's inflammation is considered inactive. Clinical outcomes and the proportion of participants that

achieve quiescence by day 7 and 21 will be compared by arm. Patients will also be administered a questionnaire querying when they felt symptomatic improvement in their condition. This analysis will be viewed as hypothesis generating and will be treated as supplementary and in addition to the main finding.

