### Primary Analysis Trial II

**Aim 2a. Recurrence rate of anterior uveitis over 12 months:** The proposed analysis for sub-Aim 2a (Trial II), which is a clinical outcome, is a log-binomial regression model to compare cumulative inflammatory recurrence (based on anterior chamber cell  $\geq 1+$  cell) between treatment groups. We will censor participants at the first recurrence of anterior uveitis (based on anterior chamber cell  $\geq 1+$  cell) or 12 months. The model includes indicators for the treatment arm and indicators for each site used to stratify the randomization. We will estimate the risk ratios from the model for the two primary comparisons, *oral valganciclovir* vs. *topical ganciclovir 2%*, and *oral valganciclovir* vs. *placebo*. We will use a simulation-based permutation test to estimate p-values, and will report max-T simultaneous confidence intervals and p-values adjusted for the two pair-wise comparisons (*oral valganciclovir* vs. *topical ganciclovir 2%*, *oral valganciclovir* vs. *placebo*). Pre-specified sub-group analyses by sex will be performed.

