### Sensitivity Analyses

In all analyses, model adequacy will be checked by examination of residuals or other goodness of fit tests as needed. Inadequate model fit will prompt us to report alternative models. If there are chance imbalances in prognostic baseline patient characteristics, including age, sex, and prednisolone use prior to enrollment, a secondary analysis will include them as covariates in the regression model.

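### Trial II has no rule for topical corticosteroid, which acts on its graded endpoint, and the SAP's only adjustment for it is conditional and secondary; the likely effect is dilution of the Aim 2a contrast

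*Protocol*

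**What the plan says.** - **Steroid start.** In the Protocol synopsis schema (Trial I, Exam 0): "Patients will be prescribed topical corticosteroid (prednisolone acetate 1%) to be used one drop in affected eye four times per day". No duration, taper or stop appears in either document.
- **Trial II entry.** Protocol 5.1 asks for less than 1+ cell for at least two weeks and: "Have a period of 2 weeks of no antiviral prior to long-term treatment initiation". The matching exclusion in 5.2 is "Did not have a 2-week period of no antiviral (treatment) prior to randomization to long-term prophylaxis". Neither mentions topical corticosteroid. The corticosteroid exclusions in 5.2, such as "Current use of oral corticosteroids", stand under Trial I and concern oral, periocular and intraocular routes.
- **Direct entry.** Protocol 4.1 states that "patients with known CMV anterior uveitis, but who are inactive, may enter Trial II directly". These participants need not have had the Exam 0 prescription.
- **Endpoint.** SAP 6.1 defines the Trial II primary event as 1+ or more "anterior chamber cell at any study visit) over 12 months". Steroid use is not part of the definition.
- **Primary model.** SAP 6.2, Aim 2a: "The model includes indicators for the treatment arm and indicators for each site used to stratify the randomization". No other covariate is listed.
- **The one provision.** The Sensitivity Analyses paragraph of SAP 6.2 says that, on chance imbalance in prognostic characteristics including age, sex and "prednisolone use prior to enrollment, a secondary analysis will include them as covariates in the regression model". It does not say whether enrolment means Trial I or Trial II.

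**The concern.** The plan washes out the antiviral before Trial II but leaves open the drug that acts most directly on what is graded. Two kinds of misclassification follow from the text as written.

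- **Masked flares.** Anterior chamber cell of 0.5+ counts as inactive. If steroid is started or increased for an emerging flare and the eye stays below 1+, the participant is scored as having no recurrence and stays in follow-up. If masking removes a constant share of recurrences, it takes the most events from the arm that recurs most.
- **Taper flares.** Nothing prevents the two weeks of inactivity at entry from being reached on steroid. A flare on later withdrawal counts as a recurrence, whatever the arm.

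Both shrink the difference that Aim 2a is meant to detect. At the SAP's design alternative, Trial II has no power in reserve.

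**Working it through.** **Inputs.** From SAP 3.3: 28 per arm, two-sided alpha 0.05/2 = 0.025 (z = 2.241), 80% power, recurrence 25% on placebo and 65% on oral valganciclovir. The same section cites observational one-year risks of 3/12 = 25% without antiviral treatment and 9/12 = 75% with systemic antivirals. The masking and taper shares below are assumptions; the documents give none.

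**Formula.** Two-sample z-test with pooled variance under the null:

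power = Φ{ [ |p2 − p1|√n − z√(2p̄(1 − p̄)) ] / √(p1(1 − p1) + p2(1 − p2)) }

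**The plan's own figure.** p1 = 0.25, p2 = 0.65, p̄ = 0.45, n = 28:
- 0.40 × √28 = 2.117
- 2.241 × √(2 × 0.45 × 0.55) = 1.577
- √(0.1875 + 0.2275) = 0.644
- (2.117 − 1.577)/0.644 = 0.838, so power = 79.9%

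The SAP's 40 points reproduces. Protocol 8.2 gives 36 points for the same inputs, which yields 69.7% power. That is a separate discrepancy, and I use the SAP's figure here.

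**Masked flares.** If a share s of true recurrences stays below 1+ in every arm, the observed risk is p(1 − s).

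**Taper flares.** If a share q of participants has an arm-independent taper flare, the observed risk is 1 − (1 − p)(1 − q).

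In each case the observed difference is the true difference times (1 − s) or (1 − q).

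| Assumed share | Masked: observed risks | Power | Taper: observed risks | Power |
|---|---|---|---|---|
| 0% | 25 v 65% | 79.9% | 25 v 65% | 79.9% |
| 10% | 22.5 v 58.5% | 70.5% | 32.5 v 68.5% | 68.6% |
| 20% | 20 v 52% | 60.6% | 40 v 72% | 57.2% |
| 30% | 17.5 v 45.5% | 50.6% | 47.5 v 75.5% | 46.3% |

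With both at 10%, and taper flares confined to participants who would not otherwise recur, the observed risks are 30% v 62% and power is 56.7%.

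**The same shares from the cited 25% v 75%.** Base power is 96%. With 10%, 20% or 30% of either kind, it is 90%, 81% and 71%. The two mechanisms agree here because 25% and 75% are symmetric about one half.

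**The case against.** Several stronger readings are tempting, and the documents do not support them.

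- **That no analysis accounts for the steroid.** SAP 6.2 does name prednisolone, in a paragraph that opens by covering all analyses. It is not limited to a yes/no variable, and direct entrants mean that it can vary. But it is conditional on imbalance, secondary, and confined to use before enrolment, so it does not reach steroid use during the 12 months.
- **That nothing in the SAP would reveal the problem.** Aim 2b tests aqueous at recurrence to separate CMV-associated flares from sterile inflammation, so CMV-negative taper flares could show there. The Kaplan-Meier curves in Aim 2c could show flares bunched soon after entry. Neither can show a masked flare, which never becomes an event.
- **That the steroid biases the arms.** The Exam 0 prescription is described as usual care, and Trial II is re-randomised 1:1:1 within site and double-masked. Steroid carried in is balanced in expectation. Bias would need steroid use after re-randomisation to differ by arm. The documents neither show nor exclude that.
- **That Trial II has only 50 to 60% power.** The shares are assumed, and 65% is the detectable rate at 80% power, not the rate observed in the cited data. The 25% may already include steroid effects, since the SAP does not say how steroid was handled in the cited study; subtracting them again could double count.

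It is also fair that no passage provides for steroid escalation at 0.5+, and that symptomatic participants are to be seen promptly (within 3 days in Protocol 8.3, 1 to 2 days in SAP 6.1). That limits masking but does not rule it out, since nothing says what happens to an eye found below 1+.

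**Conclusion.** The point holds as a gap in the Trial II rules and in the pre-specified analysis. Topical corticosteroid has no stated end, no Trial II entry, conduct or endpoint rule covers it, and the only provision in the analysis is a conditional secondary covariate tied to an unspecified enrolment. The expected consequence is a diluted contrast and some loss of power; a biased comparison is not demonstrated.

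The size cannot be computed from the documents. Under assumed shares of 10 to 30% of one kind alone, power falls from 79.9% to between 71% and 46% at the SAP's 25% v 65%, and from 96% to between 90% and 71% at its cited 25% v 75%. These figures assume equal shares in every arm and 28 evaluable participants per arm. They illustrate sensitivity and do not forecast the trial's power. The gap is worth closing because most of the change is in the SAP and because steroid use not recorded at the time may be hard to reconstruct.

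**What to change.** 1. In SAP 6.2, replace the imbalance-triggered prednisolone adjustment for Aim 2a with a pre-specified baseline covariate: topical corticosteroid use in the study eye at Trial II re-randomisation (yes/no). State a fallback in case the log-binomial model does not converge.
2. Pre-specify a sensitivity analysis of Aim 2a in which a start or increase of corticosteroid in the study eye for presumed flare counts as a recurrence.
3. Confirm that the concomitant-medication data entered in REDCap (Protocol 11.1) capture this at Trial II Exam 1 and at follow-up visits. Neither the Schedule of Activities nor the form list in Protocol 7.1.3 shows a concomitant-medication form, and the Baseline History Form is listed for Trial I only.
4. The sponsor's clinicians should reconcile the Exam 0 prescription with Protocol 5.1 and 5.2, so that the text says what steroid state inactive disease assumes. The choice is theirs.

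**Cost.** One model term, one sensitivity table and possibly one data field. The term adds some risk of non-convergence. In simulations with half of participants on steroid at entry and an assumed odds ratio of 5 or 10 for recurrence, the covariate added about 4 or 7 points of power, and the log-binomial fit reached its boundary in about 7% or 18% of trials, before site terms.

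**Limits.** The covariate recovers some precision but does not undo misclassified outcomes. The sensitivity analysis addresses masked flares only, not taper flares.
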